11.3 Study Termination

Although Oscotec Inc. has every intention of completing the study, Oscotec Inc. reserves the right to discontinue the study at any time for clinical or administrative reasons.

The end of the study is defined as the date on which the last subject completes the last visit (includes follow-up visit).

LOCF	last observation carried forward
LOF	lack of fit
LS	least-square
MCP	metacarpophalangeal
MedDRA	Medical Dictionary for Regulatory Activities
MAR	missing at random

Abbreviation	Definition
MCMC	Markov Chain Monte Carlo
MI	multiple imputation
miITT	modified intent-to-treat
MNAR	missing not at random
MMRM	Mixed model repeated measure
Npts	number of data points
PD	pharmacodynamic(s)
PIP	proximal interphalangeal
PK	pharmacokinetic(s)
PP	per protocol
PT	preferred term
PtGA	subject's global assessment for disease activity
RA	rheumatoid arthritis
RAUC	accumulation ratio
R _{met}	metabolite ratio
Rsq (r ²)	coefficient of determination
SAE	serious adverse event
SAP	statistical analysis plan
SD	standard deviation
SE	standard error
SJC	swollen joint count
SOC	system organ class
t _{1/2}	apparent terminal elimination half-life
t _{1/2,eff}	effective half-life
TEAE	treatment-emergent adverse event
TE _{max}	Time to achieve maximum effect
TJC	tender joint count
T _{max}	time to reach maximum observed concentration
TNF α	tumor necrosis factor alpha
VAS	visual analog scale
WHODD	World Health Organization Drug Dictionary

1. Introduction

This Statistical Analysis Plan (SAP) describes the analyses and data presentations for Oscotec's protocol OSCO-P2201 "A Phase 2, Multicenter, Randomized, Double-Blind, Placebo-Controlled, Parallel Dose Study to Evaluate the Efficacy and Safety of Oral SKI-O-703 in Patients With Active Rheumatoid Arthritis Despite Treatment With Conventional Therapies" which was originally issued on 20 Dec 2017, and subsequently amended on 19 Oct 2020 (Version 5.0; Amendment 4.0). It contains definitions of analysis populations, derived variables and statistical methods for the analysis of efficacy, safety, pharmacokinetics (PK) and pharmacodynamics (PD).

There is only one final analysis for this study and no interim analyses are planned. Throughout this SAP, the treatment groups will be referred to as the 100 mg twice daily (BID) group, the 200 mg BID group, the 400 mg BID group and the placebo group. The purpose of the SAP is to ensure the credibility of the study findings by pre-specifying the statistical approaches to any data analysis prior to database lock. This SAP will be finalized and signed prior to the final database lock.

All statistical analyses detailed in this SAP will be conducted using SAS® 9.3 or later (SAS Institute Inc., Cary, North Carolina).

2. Objectives

2.1. Primary Objective

The primary objective of this study is to evaluate the efficacy of select (100 mg BID, 200 mg BID, and 400 mg BID) doses of SKI-O-703 compared with placebo in subjects with active RA who have had an inadequate response to conventional synthetic disease modifying antirheumatic drugs (csDMARDs) or anti-TNF α biologic agents.

2.2. Secondary Objective

The secondary objectives of this study are as follows:

- To evaluate the efficacy on other clinical endpoints of select (100 mg BID, 200 mg BID, and 400 mg BID) doses of SKI-O-703 compared with placebo in subjects with active RA who have had an inadequate response to csDMARDs or anti-TNF α biologic agents.
- To evaluate the safety and tolerability of select (100 mg BID, 200 mg BID, and 400 mg BID) doses of SKI-O-703 compared with placebo in subjects with active RA who have had an inadequate response to csDMARDs or anti-TNF α biologic agents.
- To investigate the PK profile of SKI-O-592 (the free base of SKI-O-703) and its metabolites (M2 and M4) in subjects with active RA who have had an inadequate response to csDMARDs or anti-TNF α biologic agents.
- To evaluate the effects of SKI-O-703 on exploratory PD biomarkers (i.e., the percentage of activated gp53/CD63 $+$ basophils in peripheral blood) in subjects with active RA who have had an inadequate response to csDMARDs or anti-TNF α biologic agents.

2.3. Exploratory Objective

The exploratory objective of this study is as follows:

- To evaluate the PK/PD relationship between plasma concentrations of SKI-O-592, M2, and M4 and the percent change in activated gp53/CD63 $+$ basophils in peripheral blood in subjects with active RA who have had an inadequate response to csDMARDs or previous anti-TNF α biologic agents.

3. Investigational Plan

3.1. Overall Study Design and Plan

This is a randomized, double-blind, multicenter, placebo-controlled, parallel dose study to evaluate the efficacy, safety, tolerability, PK, and PD of select (100 mg BID, 200 mg BID, and 400 mg BID) doses of SKI-O-703 in subjects with RA who have had an inadequate response to csDMARDs or anti-TNF α biologic agents.

Approximately 148 subjects are planned to participate in 4 cohorts (37 subjects each). Subjects will be randomly assigned using a 1:1:1:1 ratio to receive one of the three doses of SKI-O-703 (100 mg BID, 200 mg BID, or 400 mg BID) or placebo. Dosing will be twice daily for 12 weeks.

The duration of study participation for a subject is up to approximately 20 weeks and the study consists of 3 periods (screening period, 12-week treatment period and 4-week follow-up period). A schematic diagram of the overall study design is presented in [Figure 3-1](#).

Figure 3-1 Study Design Schematic

Screening Period (up to 28 days)	12-Week Treatment Period (Double-Blind) 1:1:1:1							Follow-up (EOT+14 days)	EOS (EOT+28 days)
	100 mg BID								
	200 mg BID								
	400 mg BID								
	Placebo BID								
Week	0 ^a	2	4	6	8	10	12	14	16
Visit	1	2	3		4		5 (EOT)	6	7

Abbreviation: BID, twice daily; EOT, end-of-Treatment; EOS, end-of-Study

^a randomization

Screening Period

Screening assessments or procedures will be conducted up to 28 days prior to the start of study treatment. After signing and dating the informed consent form (ICF), all the potential subjects will be assessed as per the eligibility criteria at screening. After completing all screening assessments, subjects who meet all the inclusion and none of the exclusion criteria will proceed to the treatment period.

12-week Treatment Period

On Day 1, the subject will complete the Patient's Global Assessment of Disease Activity, the Patient's Assessment of Pain and the Health Assessment Questionnaire before site personnel perform any clinical assessments. After that, subject's eligibility will be confirmed and baseline safety evaluations will be performed (12-lead ECG, physical examination, vital sign measurements, weight, urine pregnancy test, and safety laboratory assessment). Following

predose study procedures, they will be randomized to receive either SKI-O-703 or placebo. On Day 1, subjects will be administered his/her first dose of study medication no later than 30 minutes after food with approximately 8 ounces (240 mL) of water by the site personnel.

A subset of subjects from each cohort who provide additional consent will be subjected to additional PK and PD assessments according to the Schedule of Events ([Appendix 15.1](#)). Due to PD assay limitations, PK and PD sampling will only be performed at selected sites that are deemed suitable to support PK/PD assessment (ie, which are within an acceptable shipping distance from a PD laboratory). Every effort will be made to achieve a minimum of 24 subjects (6 subjects per treatment group) in the PK/PD subgroup. It is important to note that there is no upper limit to the number of subjects that will be enrolled to the PK/PD subgroup in any region (as many subjects will be assigned to the PK/PD subgroup as is practical), and the number of subjects does not need to be identical between treatment groups.

The second dose will be administered approximately 12 hours (± 2 hours) after the first dose. The second dose and all subsequent doses, will be self-administered by the subject. The subjects will be instructed to take study medication no later than 30 minutes after food. Subjects will return to the clinic for routine safety and disease state review as outlined in the Schedule of Events, with a ± 3 days window for all visits after randomization.

During the visits after Day 1, subject will undergo the procedures at the timepoints as specified in the Schedule of Events. The subject should complete the Patient's Global Assessment of Disease Activity, the Patient's Assessment of Pain and the Health Assessment Questionnaire before site personnel perform any clinical assessments. These should also be completed before any interaction with site personnel has occurred to avoid biasing the subject's response.

4-week Follow-up Period

All subjects who complete the treatment period, as well as subjects who discontinue the treatment at any time for any reason, are to enter the 4-week Follow-up period after the EOT visit.

3.2. Study Endpoints

3.2.1. Primary Endpoint

- Mean change from baseline in disease activity score in 28 joints (DAS28) using high sensitivity C-reactive protein (hsCRP) (based on 3 individual components including TJC, SJC and hsCRP) at Week 12

3.2.2. Secondary Endpoints

The secondary efficacy endpoints will be evaluated at Week 2, 4, 8 and 12 unless otherwise stated.

- Percentage of subjects who would achieve American College of Rheumatology (ACR) response (ACR20, ACR50 and ACR70) over time
- Change from baseline in DAS28-hsCRP score (based on 3 individual components including TJC, SJC and hsCRP)

- Change from baseline in the tender/painful and swollen joint count (28)
- Change from baseline in the physician global assessment of disease activity by visual analog scale (VAS)
- Change from baseline in the subject global assessment of disease activity by VAS
- Change from baseline in the subject assessment of arthritis pain by VAS
- Change from baseline in the health assessment questionnaire - disability index (HAQ-DI)
- Change from baseline in median hsCRP values at each schedule visit
- Safety and tolerability of SKI-O-703 compared to placebo including laboratory tests, infections, ECGs, vital signs, incidence of AEs, withdrawals due to AEs and serious adverse events (SAEs).
- PK parameters of SKI-O-592 and its metabolites (M2 and M4) from a subset of subjects per cohort on Day 1 and at Week 12, including: C_{max} , T_{max} , AUC_{0-tau} , $t_{1/2,eff}$, R_{met} , and R_{AUC} , as applicable
- PD parameters for the change from baseline in the percentage of activated gp53/CD63+ basophils in peripheral blood on Day 1 and at Week 12, including: E_{max} , TE_{max} , $AUEC_{0-tau}$, as applicable

3.2.3. Exploratory Endpoints

- An assessment of PK/PD relationship between plasma concentrations of SKI-O-592, M2, and M4 and change from baseline in the percentage of activated gp53/CD63+ basophils in peripheral blood on Day 1 and at Week 12

4. General Statistical Considerations

4.1. Reporting Convention

- Summary statistics will consist of the number and percentage of subjects in each category for discrete variables, and the sample size, mean, median, standard deviation (SD), minimum and maximum for continuous variables.
- All mean, median values and confidence intervals will be formatted to one more decimal place than the measured value. Standard deviations and standard errors will be formatted to two more decimal places than the measured value. Minimum and maximum values will be presented to the same number of decimal places as the measured value. The maximum decimal places will be set to 4.
- Frequency summary for categorical variables includes number and percentage. All percentages will be rounded to one decimal place. Number and percentage values will be presented as xx (xx.x). If the percentage is 100, no decimal is required.
- P-values will be formatted to 3 decimal places; if a p-value is less than 0.001, it will be displayed as <0.001.
- All analysis and summary tables will have the population sample size for each treatment group in the column header if appropriate. All the subject data listings will be presented by treatment group and subject identifier where applicable.
- All programmatically calculated values (e.g. treatment compliance) will retain all decimal places at the Analysis Data Model (ADaM) level. For reporting purpose in listings and summary tables, up to 1 decimal place will be retained for raw values, minimum and maximum. Other summary statistics will then follow the same incremental precision rules specified above
- The day of the first dose of any study drug will be defined as Study Day 1. Study Day are calculated relative to Study Day 1, as the difference between the date of interest and Study Day 1, and plus 1 day additionally if date of interest is on or after Study Day 1.

For PK and PD analysis, the reporting convention is specified in the corresponding [Section 10](#) and [Section 11](#). The above convention is applied to all efficacy and safety analyses.

4.2. Baseline Definition and Visit Window

Baseline value is defined as the last non-missing value on or before the date of the first dose of study drug. For subjects who were not treated, the baseline will be the assessment value taken on the screening visit, on or before the randomization day.

There is no separated visit folder designed in EDC for the treatment early terminated visit and the visit folder 'Visit 5 EOT' will serve as both the visit at Week 12 and the early terminated visit. Therefore, the assessments captured under visit folder 'Visit 5 EOT' will be summarized under visit Week 12 only when the subjects completed the treatment period; otherwise, 'Visit 5 EOT' will be treated as the treatment early terminated visit. There is no other visit mapping

performed and all the by-visit summaries will be based on the nominal visit as collected on the eCRF page except the visit handling of ‘Visit 5 EOT’.

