1.4 Placebo Rationale

The proposed study is a placebo-controlled, double-blind study of oral SKI-O-703 coadministered with background therapies for RA. The double-blind, placebo-controlled, randomized clinical study design is considered the gold standard for the safety and efficacy assessment of a new therapy both by clinicians and regulatory authorities. In this study subjects will be allowed to receive background medications for RA, including MTX, and other oral DMARDs, therefore subjects are also allowed to receive permitted concomitant medications in line with current standard of care (SOC) practices for RA. Any subject who cannot adhere to the protocol or who discontinues treatment will have an end-of-treatment (EOT) and will be followed for the intended duration of the study.

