4.2.2 Handling of Withdrawals

Subjects who discontinue study treatment or active participation in the study will no longer receive study drug. When a subject withdraws from the study, the reason(s) for withdrawal shall be recorded by the investigator on the relevant page of the eCRF. Whenever possible, all subjects who discontinue study drug or withdraw from the study prematurely will undergo all end-of-study assessments.

Subject who choose to discontinue study drug treatment but continue to participate in the study should complete end of treatment visit as soon possible, preferably within 2 weeks. Afterwards, subjects should follow the regular visit schedule and adhere to all study procedures except for dispensing study drug and blood sample collection for optional exploratory research and validation studies.

Subjects who fail to return for final assessments will be contacted by the site in an attempt to have them comply with the protocol. Following a minimum of 2 documented unsuccessful telephone calls, a registered letter will be sent to the subject in a final attempt to ensure protocol compliance.

It is vital to obtain follow-up data on any subject withdrawn because of an AE or serious AE (SAE). In every case, efforts must be made to undertake protocol-specified, safety, follow-up procedures.

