5.4.2 Test Article Accountability

The investigator or pharmacy designee will maintain accurate records of receipt of all test articles, including dates of receipt from sponsor, assignment and dispensation to the subject(s), return from subject(s), and destruction of returned IMP (and/or return to the depot for destruction). This is denoted as pharmacy IMP accountability.

In addition, accurate records will be kept by the responsible site personnel regarding when and how much test article is dispensed to, used by, and returned from each subject in the study. At each study visit requiring dispensation (Visit 1, 3, and 4), a new set of 4 bottles of IMP will be dispensed to the subject to cover that study visit period and the previous set of 4 bottles will be collected. Subject dosing will be recorded on a subject dosing diary. Subjects will be instructed to return all drug containers (even if empty) to the study site personnel at each clinic visit. Site personnel will document compliance and reasons for departure from the expected dispensing regimen in study source documents. This is denoted as subject IMP accountability.

At the completion of the study, to satisfy regulatory requirements regarding drug accountability, all study drugs will be reconciled and retained or destroyed according to applicable regulations.

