6.1 Study Visits

The schedule of events is summarized in Table 6-1.

Table 6-1
Schedule of Events

Procedure ^a	Screening	Baseline	Treatment Period			EOT	Follow-up	EOS ^b
Visit ^c	1	2	3	4	5	6	7	
Study Day	Day-28 to -1	Day 1 ^d	Day 14 (±3 days)	Day 28 (±3 days)	Day 56 (±3 days)	Day 84 (±3 days)	Day 98 EOT+14 days (±3 days)	Day 112 EOT+28 days (±3 days)
Study Week	0	2	4	8	12	14	16	
GENERAL ASSESSMENTS								
Informed consent	X							
Inclusion/exclusion criteria	X	X						
Demographics	X							
Medical/surgical history	X							
Alcohol and nicotine use	X							
Height	X							
Weight	X	X				X		X
Physical examination ^e	X	X				X		X
Vital sign measurements ^f	X	X	X	X	X	X		X
Adverse event monitoring	X	X	X	X	X	X		X
Concomitant medications	X	X	X	X	X	X		X
Prior medications	X							
RA ASSESSMENTS								
Tender/painful and swollen joint counts (TJC28/SJC28)	X	X	X	X	X	X		X
Physician/patient's global assessments of disease activity ^g		X	X	X	X	X		X
Patient assessment of general health ^h		X	X	X	X	X		X
Patient assessments of arthritis pain ^g		X	X	X	X	X		X

Procedure ^a	Screening	Baseline	Treatment Period			EOT	Follow-up	EOS ^b
Visit ^c	1	2	3	4	5	6	7	
Study Day	Day-28 to -1	Day 1 ^d	Day 14 (±3 days)	Day 28 (±3 days)	Day 56 (±3 days)	Day 84 (±3 days)	Day 98 EOT+14 days (±3 days)	Day 112 EOT+28 days (±3 days)
Study Week		0	2	4	8	12	14	16
HAQ-DL ^g	X	X	X	X	X	X	X	X
Randomization/drug assignment	X							
INVESTIGATIONAL PRODUCT ADMINISTRATION								
Dispense study drug and subject dosing diary		X		X	X	X		
Study drug administration		X	X	X	X	X	X	
Review and copy subject dosing diary and perform drug reconciliation			X	X	X	X		
CENTRAL LABORATORY EXAMINATIONS								
HBsAg, HBCaB, HCV, and HIV tests	X							
QuantiFERON Gold - tuberculosis test ^h	X							
Serum pregnancy test ⁱ	X							
FSH level	X	X						
Urine pregnancy test ⁱ		X	X	X	X	X	X	X
Hematology ^j	X	X	X	X	X	X	X	X
Coagulation	X	X	X	X	X	X	X	X
Chemistry ^j	X	X	X	X	X	X	X	X
Urinalysis	X	X	X	X	X	X	X	X
hsCRP ^k	X	X	X	X	X	X	X	X
IMAGING								
Chest x-ray ^l	X							
12-lead electrocardiogram ^m	X	X	X	X	X	X	X	X
SUBSTUDY								

Procedure ^a	Screening	Baseline	Treatment Period			EOT	Follow-up	EOS ^b
Visit ^c		1	2	3	4	5	6	7
Study Day	Day-28 to -1	Day 1^d	Day 14 (±3 days)	Day 28 (±3 days)	Day 56 (±3 days)	Day 84 (±3 days)	Day 98 EOT+14 days (±3 days)	Day 112 EOT+28 days (±3 days)
Study Week		0	2	4	8	12	14	16
Blood sampling for PK ^e		X	X	X	X	X		
Blood sampling for PD (CD63 + basophils) ^f		X	X	X	X	X		

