Abbreviations: ACR, American College of Rheumatology; CD63, cluster of differentiation 63; DAS, disease activity score; EDTA, ethylenediaminetetraacetic acid; EOS, end-of-study; EOT, end of treatment; FSH, follicle-stimulating hormone; HBsAg, hepatitis B surface antigen; HIV, human immunodeficiency virus; HAQ-DI, Health assessment questionnaire disability index; HBcAb, hepatitis B core antibody; HCV, hepatitis C virus; hsCRP, high sensitivity C-reactive protein; PD, pharmacodynamic; PK, pharmacokinetic; PPD, purified protein derivative; RA, rheumatoid arthritis; TB, tuberculosis; WOCBP, women of child bearing potential.

^a When procedures overlap at the same timepoints, the vital parameters assessment will be performed first followed by laboratory parameters and other procedures (Section 6.4.2).

^b Subject who choose to discontinue study treatment, but continue to participate in the study should complete EOT visit as soon possible, preferably within 2 weeks. Afterwards, subjects should follow the regular visit schedule and adhere to all study procedures except for dispensing study drug, and blood sample collection for optional exploratory research and validation studies.

^c Any of the procedures may be performed at an unscheduled visit at the discretion of the investigator.

^d All study procedures on Day 1 must be completed prior to randomization in order to save time for IMP dispensation and postdose PK/PD sampling.

^e A complete physical examination should be performed at the time points specified. Interim physical examinations can be performed at the discretion of the investigator, if deemed necessary to evaluate AEs or clinical laboratory abnormalities (Section 6.4.1).

^f Vital sign measurements include systolic and diastolic blood pressure, pulse rate, respiratory rate, and oral temperature (tympanic temperature for Korean subjects). The subject must be seated for 5 minutes before all measurements are taken (Section 6.4.2).

^g Patient questionnaires and scales should be performed prior to any procedures and assessments. The HAQ-DI should be scored for all 8 categories (Section 6.3.3).

^h TB testing will be performed for all subjects within 28 days of Day 1. Positive diagnostic TB test, which is defined as positive QuantiFERON Gold test will be tested in central laboratories for all subjects and will determine subject's eligibility with regards to TB.

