6.8 Pregnancy

Subjects must be counseled during the informed consent process to inform the investigator of any pregnancy that occurs during study participation and for 6 months after the last dose of study drug. In the event of an unexpected pregnancy during study participation or for 6 months after the last dose of study drug, it must be reported via fax or email to PPD within 24 hours of the study site knowledge of the pregnancy via manual Initial Pregnancy Report Form.

For a female subject, the study drug must be discontinued immediately and the subject should inform the Investigator as soon as possible (see Section 4.2). Although study drug will be discontinued, the subject may choose to remain in study and will continue to be monitored for safety while following their regular visit schedule. If the partner of a male subject becomes pregnant, the male subject is not required to discontinue study drug and may remain on the study. The male subject is responsible for informing his partner(s) of the risk of becoming pregnant and for reporting any pregnancy to the Investigator.

The pregnancy must be followed up to determine the outcome (including spontaneous miscarriage, elective termination, normal birth, or congenital abnormality) and the status of mother and child, even if the subject was discontinued from the study, and should be reported to PPD via fax or email on the manual follow-up pregnancy form.

Pregnancy complications and elective terminations for medical reasons must be reported as AEs or SAEs. Spontaneous miscarriages must be reported as SAEs.

Any SAE occurring in association with a pregnancy that is brought to the Investigator's attention after the subject has completed the study and that is considered by the Investigator as possibly related to the study drug must be promptly reported to the sponsor.

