8.2.1. Primary Analysis

The primary analysis will be conducted on observed cases, which means DAS28-hsCRP at Week 12 will be calculated only when all the three individual components (TJC28, SJC28 and hsCRP) are assessed at this visit; otherwise, DAS28-hsCRP at Week 12 will be considered as missing.

The change from baseline in DAS28-hsCRP at visit Week 12 will be analyzed using an analysis of covariance (ANCOVA) model. The model will include treatment groups as a factor and DAS28-hsCRP at baseline as a covariate. Within-group least-square (LS) means and the associated standard errors (SE), the treatment differences in LS means and the associated SEs, the 2-sided 95% CIs, the 2-sided p-values for treatment comparisons between each of active treatment group and placebo group, and the 2-sided p-values for treatment comparisons among active treatment groups (high dose vs. low dose) will be estimated and provided. Descriptive statistics of baseline, observed value and change from baseline at Week 12 will be summarized by treatment group.

The primary efficacy analyses will be performed based on the ITT set, and then repeated using the PP set.

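### SAP 4.2 gives a Day 84 assessment made after stopping drug no stated route into the primary observed-case Week 12 ANCOVA, and the documents disagree on whether that visit takes place

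*SAP*

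**What the plan says.** **Mapping.** SAP 4.2 says that Visit 5 EOT serves as both the Week 12 visit and the early-termination visit. Its assessments "will be summarized under visit Week 12 only when the subjects completed the treatment period"; otherwise they are the early-termination visit. Every other by-visit summary uses the nominal visit on the eCRF. SAP 5.1 contrasts completing the treatment period with discontinuing it, so a subject who stops drug is a non-completer.

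**Primary analysis.** SAP 8.2.1 fits the ANCOVA to the ITT set (randomized and dosed, SAP 4.5): "The primary analysis will be conducted on observed cases, which means DAS28-hsCRP at Week 12 will be calculated only when all the three individual components" are assessed.

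**Visits after stopping drug: text that suggests Day 84 is kept.**
- Protocol 1.4: a subject "who discontinues treatment will have an end-of-treatment (EOT) and will be followed for the intended duration of the study".
- Protocol 4.2.2, for those who stop drug but stay in the study, after an EOT visit: "Afterwards, subjects should follow the regular visit schedule and adhere to all study procedures except for dispensing study drug".
- Table 6-1 footnote b says the same: "Subject who choose to discontinue study treatment, but continue to participate in the study should complete EOT visit" and then return to the regular schedule.

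**Text that suggests follow-up begins at once.**
- Protocol 3.1 has subjects complete a 4-week follow-up after the EOT visit.
- SAP 3.1 says this expressly of subjects who discontinue treatment at any time.
- Table 6-1 labels the last two visits both as Days 98 and 112 and as EOT+14 and EOT+28 days.

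**The concern.** Keeping an early-termination assessment from being called Week 12 is right. The difficulty is that the rule looks at treatment status and not at when the assessment was made, so it also removes a genuine Day 84 assessment from a subject who stopped drug and stayed.

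That makes inclusion in an analysis labelled ITT depend on an event after randomization. Protocol Table 3-1 prescribes permanent discontinuation for several adverse events, so stopping may differ between arms and the exclusion may not be random. The sample size counts subjects who complete the study. A subject who stops drug but stays can count toward the 37 per arm and still be absent from the primary comparison.

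The SAP does state a rule for visits after treatment discontinuation for the DAS28 binary endpoints (SAP 8.4). For the primary endpoint it never says whether such values are meant to be left out.

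**Working it through.** **1. Can the Day 84 value reach Week 12?** The EDC build is not in the documents, so take each way the value could be recorded and apply SAP 4.2.

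| Where Day 84 is recorded | Result under SAP 4.2 |
|---|---|
| Early EOT already fills Visit 5 EOT | No label left for Day 84 |
| Day 84 is entered in Visit 5 EOT | Labelled early termination, because treatment was not completed |
| Unscheduled visit (allowed by Table 6-1 footnote c) | Nominal visit is not Week 12; no mapping |

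None leads to the ANCOVA.

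**2. Other analyses of DAS28-hsCRP.**
- LOCF (SAP 8.2.2) fills Week 12 by carrying a value forward.
- Multiple imputation (SAP 8.2.3 and 8.2.4) imputes it.
- The ITT MMRM (SAP 8.3.1) uses nominal visits, so off-drug Week 2, 4 and 8 values enter it and inform its Week 12 estimate. The Day 84 value does not.

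Only Week 12 depends on treatment completion. A subject who stops in Week 3 and attends every visit contributes off-drug values at Weeks 4 and 8 and none at Week 12.

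**3. Is the Day 84 visit planned?** The exception for dispensing in protocol 4.2.2 fits treatment-period visits, because by protocol 5.4.2 drug is given out only then: "At each study visit requiring dispensation (Visit 1, 3, and 4), a new set of 4 bottles of IMP will be dispensed". Against this, the two sets of labels in Table 6-1 agree only if EOT is Day 84 (98 − 84 = 14; 112 − 84 = 28). If follow-up is anchored to EOT, the last visit is at latest EOT + 31 days. It precedes the Week 12 window (Day 81 to 87) when EOT + 31 < 81, that is, when EOT is before Day 50. The text does not settle which is meant.

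**4. The plan's own figure.** Inputs from SAP 4.3: difference 0.8, SD 1.25, 37 per arm, two-sided 0.05. The standard error of one pairwise difference is 1.25 × √(2/37) = 0.291. Normal-approximation power is Φ(0.8/0.291 − 1.96) = 0.786. The overall four-group ANOVA F test with one group differing by 0.8 gives 0.806, which matches the stated 0.80. The sample size is not in question.

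**5. Size of the shift.** Suppose k of the 37 subjects in one arm with a Day 84 assessment are off drug, and their mean change differs by g from that of the arm's completers. Leaving them out shifts the arm mean, and so the treatment difference, by (k/37) × g. Neither k nor g is in the documents. Assume k from 0 to 4 (0 to 11%) and g = 0.8.

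| k | (k/37) × 0.8 | Divided by 0.291 |
|---|---|---|
| 0 | 0 | 0 |
| 1 | 0.022 | 0.07 |
| 2 | 0.043 | 0.15 |
| 4 | 0.086 | 0.30 |

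With g = 0.4 these halve. If the omitted subjects do worse than completers, the effect is too large when they are on active drug and too small when they are on placebo. Equal numbers and gaps in both arms cancel.

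**6. Precision.** Losing 4 in each of the two compared arms gives 1.25 × √(2/33) = 0.308, which is 6% above 0.291.

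**The case against.** The strongest reply is that no such visit may be intended. Protocol 4.2.2 does not name Day 84. After an EOT visit the next columns in Table 6-1 are the follow-up visits, and footnote b appears, in the extracted table, on the end-of-study heading. The dispensing exception stands beside a reference to optional research samples that match no other procedure in the documents, which suggests template wording. The pregnancy section also keeps a subject on the schedule ("the subject may choose to remain in study and will continue to be monitored for safety while following their regular visit schedule"), but for safety, so it is no evidence of an efficacy plan. These points stand as reasons for doubt. They do not dispose of protocol 1.4, and they show why the schedule needs settling.

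It can also be said that SAP 4.2 is an explicit rule, that the analysis is openly observed-case, and that using off-drug values is a choice of what to estimate. That is fair as far as it goes. But no text presents the exclusion as such a choice, and keeping off-drug values at Weeks 2 to 8 tells against it.

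Three stronger readings are tempting and are not supported:
- *These subjects are lost from every Week 12 ITT analysis.* They are not. Multiple imputation keeps them with imputed values, and the MMRM uses their Week 2 to 8 data.
- *The SAP contradicts a clear protocol.* The protocol itself pulls both ways: section 3.1 and the EOT-anchored labels against 1.4, 4.2.2 and footnote b.
- *The 10% drop-out measures the number affected.* It allows for subjects who do not complete the study. The group here stops drug and stays.

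**Conclusion.** The point holds for the observed Day 84 value. As SAP 4.2 is written, that value cannot enter the primary observed-case ANCOVA, and the LOCF and multiple-imputation analyses would replace it although it was measured. Whether the visit takes place is itself unclear from conflicting text in both documents.

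The likely size is small: a shift of 0 to 0.09 DAS28 units, or at most 0.30 of the planning standard error, of unknown sign. The upper end needs four such subjects in one arm and none in the comparator, with a gap as large as the design effect. All of these are assumptions, and the true count may be zero. The routes in step 1 are inferred from SAP text, so confidence is medium. It should still be fixed, because it makes an ITT comparison depend on treatment completion and can be settled cheaply while the data are blinded.

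**What to change.** 1. In SAP 4.2, label the early-termination assessment as its own visit. Map any assessment in the Day 84 (±3) window to Week 12 whatever the treatment status, from whichever record holds it.
2. State in SAP 8.2 and 8.3 that these values count as observed in the ITT primary ANCOVA and in the LOCF, multiple-imputation and MMRM analyses. Leave the non-responder rules in SAP 8.3.2 and 8.4 unchanged.
3. Reconcile protocol 1.4, 3.1, 4.2.2, Table 6-1 with its footnote b, and SAP 3.1 on the visit schedule after stopping drug. This review takes no position on which schedule should apply.
4. Before database lock, report a blinded overall count of subjects who stopped drug and have an assessment in the Day 84 window.

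**Cost.** One mapping rule, a few sentences and a little programming. No new subjects and no change of model. Whether the EDC needs changing cannot be judged from the documents. Some off-drug visits may no longer be recoverable, and the estimated effect may change slightly in either direction.
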